### **6.7. Follow up and end of study**

First follow up will be conducted one month after the last dose of PQ treatment administration. Every visit, blood samples from finger prick and skin (LMS) will be taken. Unlike in the 16ecurrent process, malaria blood smear will be made only from participants with clinical symptoms suggestive for malaria. If positive, they will be treated. All treatment during follow up period will be provided by PHC staff according to national guideline (Appendix B table 1 & 3).

At the end of study (month-9 of the follow up), mass blood survey will be conducted to collect finger prick blood (LMF, Pv serological test, qPCR) and LMS. Seroconversion will be assessed. All LMF (+) will be treated as above.

All study subjects will be followed until the end of study (month 9) although they cannot fulfil the complete schedule.

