	
standard finger stick microscopic.
 
 
• In the SSAT arm at enrollment, only children who are Pv seropositive and/or LMF Pv/Po positive receive supervised high-dose primaquine (1mg/kg for 7 days) regardless of their symptoms. All blood slides will be processed and read directly after blood collection. Then treatment will follow if positive. Sero-positive children, on the other hand, will commence treatment after the result is available (approximately 1 week). Symptomatic or asymptomatic LMF positive for Pf/Pm will be treated according to current national guidelines.
 
• In the control arm at enrollment, only children who are symptomatic and LMF Pv/Po positive will receive supervised high-dose primaquine (1mg/kg for 7 days).
 
• In both arms at every other timepoint, symptomatic LMF positive children will receive treatment in accordance with national guidelines (unsupervised).
 
• In both arms at the final timepoint, LMF will be conducted on all children and if positive will be treated according to national guidelines.
 
• As blood schizontocides, DHA-PP for 3 days will be given according to body weight (national guidelines).
 

Inclusion and Exclusion Criteria
	
Inclusion:
 
 
• resident of study area and attending selected elementary school in Grade 1-5
 
• no evidence of health condition that would interfere with study participation
 
• assent of child and documented parental informed consent
 
 
Exclusion:
 
 
• G6PD deficiency as determined by SD Biosensor quantitative determination of <70% G6PD activity (male: <4 U/g Hb, female: <6 U/g Hb).
 
• Haemoglobin < 9 g/dL
 

Analysis plan and sample size calculation
	
The study is designed to show a superiority of SSAT vs. routine care for the prevention of recurrent P. vivax infections. The primary study endpoint will be the proportion of children with recurrent P. vivax by PCR during 9 months of follow-up. Secondary endpoints include time-to-first P. vivax recurrence as well as incidence of symptomatic

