	
P. vivax.
 
SSAT intervention is expected to reduce incidence of P. vivax in comparison to standard care. With the previous prevalence rate of 20%, we will have a power of >90% to detect a significant difference with the sample size of 350 children per group. We will anticipate the exclusion of 15% by recruiting 400 children per group.

Lay Summary
	
This study evaluates an experimental serological diagnostic technique intended to identify people at high risk of having dormant malaria parasites in their liver. The findings will assess the ability of this sero test to identify those carriers.
 
800 children living in eastern Indonesia will be individually randomised to the experimental serologic test or routine care.
 
Children in the serological diagnosis arm will be screened for the presence of antibodies to a previously validated panel of malaria antigens optimized for sensitivity to infection during the prior 9 months. Furthermore, they also will be screened by microscopy. If positive by either test, they will be treated for that malaria infection.
 
Children assigned to routine care will be screened by microscopic examination and treated when they show or have history of symptoms in the last 3 days.
 
After initial screening and treating according to diagnostic technique, all children will be actively followed for 9 months with PCR detection every 4 weeks.
 
During 9 month follow up, all children becoming acutely ill and proven to be positive for malaria by microscopy will be treated, in addition, all asymptomatic children will be treated at the final time point.
 
POC serology test will be performed at baseline and final timepoint on all children in both arms. The results from this POC serology test will not be used to inform diagnosis or treatment in any way at either of the timepoints.
 
None of these blood samples will be collected by venopuncture but instead minimally invasive lancet devices will be used.

Sero-diagnostic test
	
Quantitative measurement of antibody titres to a panel of 8 specially selected P. vivax antigens in study subject plasma samples using a Luminex MAGPIX® bead array system. This testing will be done at the Eijkman Institute in Jakarta. The results will be generated in no

	more than 7 days.
--	-------------------

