### **6.2. Schools selection and demographic census**

Before the start of the study, a serological survey will be conducted to select the schools. Blood samples will be collected from 20 randomly selected children from each school in Weoe for serological screening with Luminex. Only schools with sero-prevalence of 30-70% will be eligible for enrollment. Maximal number of selected schools will be 6-7, where 800 children will be individually randomized. Demographic census will be conducted during which name, date of birth/age, gender, village, hamlet, parents/guardian will be recorded (census form). Photograph will be taken from each participants to ensure the correct identification for treatment administration and follow up.

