### 6.3. Study design and study overview

The study design is a randomized controlled trial with serological screening and treatment as the intervention. Selected schoolchildren will be allocated into two study arms: (1) serological screening and treatment (SSAT), and (2) routine care as control arm.

At enrolment, in the SSAT arm, individuals found *P. vivax* positive by either serological (Luminex) or Giemsa stained microscopic examination regardless of the symptoms will receive supervised treatment (direct observation) with high dose PQ (daily 1 mg/kg BW) for 7 days ( $P_o=P_v$ ). In the control arm, only symptomatic individuals found *P. vivax* positive by Giemsa stained microscopic examination will receive the same regimen ( $P_o=P_v$ ). In addition, in the treated children of both arms, dihydroartemisinin-piperaquine (DHA-PP) will be given as blood schizontocide according to body weight. All other species (*P. falciparum*, *P. malariae*) found by Giemsa stained microscopic examination will be treated according to national guideline. Serological examination will be performed by Luminex (done at Eijkman, Jakarta) and point-of-care (POC) antibody detection using rapid test on site

Follow up will be performed monthly for 9 months. During this period, 400  $\mu$ L of finger pricked blood samples will be collected from all children in both arms. These samples will be tested for malaria presence by PCR which will be done at EO CRU, Jakarta. However, children with clinical symptoms (body temperature of  $\geq 37.5^\circ\text{C}$  and/or history of fever within 3 days), will be examined by Giemsa stained microscopy on site, and treated if positive (any species) according to national guideline (unsupervised).

At the last follow up, a mass blood survey will be conducted to both arms for *Pv* serological test, LMF, and PCR. Those found positive by LMF for any species will be treated regardless of their symptoms.

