### **6.8. Antimalarial treatment**

Treatment will be provided based on body weight (Appendix B). Blood schizonticide for any species is 3-day DHA-PP (daily dose: 6-10 kg=1/2 tab, 11-17 kg=1 tab, 18-30 kg=1 ½ tab, 31-40 kg=2 tab). For *P. vivax* subjects, the administration of high dose primaquine will be started at the same day of DHA-PP treatment (see Table 2 appendix B for PQ dosage). Meal should be given prior to PQ administration daily. The total dose of PQ should be completed within 10 days as the window period. Subjects who does not complete the dose will be recorded, and still be followed until end of study. Monitoring of Hb level and hemoglobinuria for treated subjects will be done daily before and during treatment by Hb measurement using HemoCue (HemoCue AB, Angelholm, Sweden) and urine test (inspection and urinalysis) in order to detect hemolysis. Primaquine will be stopped if hemolysis

occur, the subject will be observed for daily vital sign, Hb level, and urine until recovery. If worsen, the subject will be referred to the hospital for further management, and given blood transfusion if necessary (Appendix E).

Primaquine for *P. falciparum* will be given as single dose 0.25 mg/kgBW (6-17 kg=1/4 tab, 18-30 kg=1/2 tab, 31-40 kg=3/4 tab). *P. ovale* will be treated as *P. vivax*. Mixed infection with *Pv* will be treated as *Pv*.

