### 8.3. Data analysis

*Plasmodium vivax* incidence is defined as the total number of new genetically distinct *P. vivax* clones per child per detected during the follow up period. The analysis will use the comparison of two incidence rates between SSAT group and control group. For comparison, data will be entered as the number of recurrent *Pv* (numerators) and the total length of time people contributed in the cohort (person-time) as denominators. We will calculate the exact probabilities (Fisher's and Mid-P), the rate ratio with the exact confidence intervals and the measures of the impact of intervention. We will report the 95% of confidence interval for this comparison. Measures of the impact of intervention are computed for the prevented fractions in the exposed and in the population and the preventable fraction in the population.

As secondary endpoints, we will use Kaplan-Meier method to detect differences in the time-to-first recurrence of *Pv* by PCR in SSAT and control arms. The log-rank test is used to detect any difference between the two groups. Cox proportion hazard will be used to measure the effect size.

Multiple recurrences of *P. vivax* infections will be calculated during follow up. Number of events will be calculated, divided by the total length of time people

contributed in the cohort (person-time) as denominators. We will calculate the exact probabilities, rate ratio with the exact confidence intervals, and the measures of the impact of intervention using same tests as above.

Symptomatic recurrent *P. vivax* is defined as LMF positive with fever ( $\geq 37.5^{\circ}\text{C}$ ) or history of fever in the last 3 days during follow up. The same statistical test will be performed to compare both groups.

Difference of seropositivity between the two arms before and after the intervention will be calculated using chi-square test with p value  $< 0.05$  as limit of significance.

Sensitivity, specificity, positive predictive value, and negative predictive value of POC *Pv* antibody rapid test will be reported with Luminex as the golden standard.

Type and number of AE and SAE will recorded, and reported with total length of time people contributed in the cohort (person-time) as denominators.

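### Section 6.7 dates the first follow-up from the last primaquine dose, an event most children never have, and this does not match the single visit schedule in Appendix H

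*Protocol*

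**What the plan says.** **The rule.** Section 6.7: "First follow up will be conducted one month after the last dose of PQ treatment administration". No other sentence dates the first visit.

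**Who has a last dose.**
- Synopsis: "In the control arm at enrollment, only children who are symptomatic and LMF" positive for *P. vivax* or *P. ovale* get the supervised seven-day course.
- In the SSAT arm the course goes to children positive by serology or by slide. Slide-positive children are treated straight away; seropositive children "will commence treatment after the result is available (approximately 1 week".
- Section 6.8: "The total dose of PQ should be completed within 10 days as the window period".
- School selection (6.2): "Only schools with sero-prevalence of 30-70% will be eligible for enrollment".

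**The visit schedule.**
- Section 6.3: "Follow up will be performed monthly for 9 months".
- Synopsis: "all children will be actively followed for 9 months with PCR detection every 4 weeks".
- Sections 6.7 and 7.1.1 number the visits months 1 to 9.
- Appendix H has one table for all children: a drug block starting about day 7, then nine visits labelled Months 2 to 10.
- Appendix C shows enrolment in January-February 2020 and nine months of sampling from March to November.

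**The analysis.** Section 8.3 divides events by "the total length of time people contributed in the cohort (person-time) as denominators" and compares time to first recurrence by log-rank test and Cox model.

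**The concern.** A visit rule in a randomised comparison should apply to every randomised child and should not depend on what happened after randomisation. This one depends on the intervention itself. It is undefined for nearly all controls and for the doubly negative part of the SSAT arm. Among treated children it varies with the route to treatment (slide or serology) and with how long the course takes, and it moves again if the course is stopped early. Section 6.7 also does not say whether the single primaquine dose for *P. falciparum* counts as a last dose.

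The primary numerator is what is detected during follow-up, its denominator is person-time, and a secondary endpoint is time to first recurrence. All three depend on when sampling starts. If field teams take the sentence literally, treated children (mostly SSAT) and untreated children (mostly control) could be sampled on different dates. An analysis plan can fix the time origin later, but it cannot recover samples taken on different dates. Time to first recurrence is the more exposed endpoint, because with an enrolment origin a later first sample delays the first possible detection even when the drug does nothing.

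**Working it through.** The plan gives no figure for this point, so there is none to reproduce. The check sets out the visit dates under each reading and then the size of any distortion.

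**Inputs.** From the protocol: serology delay about 7 days (synopsis), course of 7 days or up to 10 (6.8), nine months of follow-up (6.3), eligible school seroprevalence 30-70% (6.2). Assumed: a month is 30 days, so follow-up is 9 × 30 = 270 days; untreated children are timed from enrolment; school seroprevalence stands in for the share of SSAT children treated.

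**Step 1: first visit if the rule is applied child by child.** First visit = start day + course length + 30. The lower figure in each cell counts the first dose on the start day; the higher counts elapsed days.

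| Child | Last dose | First visit | Later than day 30 by |
|---|---|---|---|
| Slide-positive, starts day 0 | day 6-7 | day 36-37 | 6-7 days |
| Seropositive, 7-day course | day 13-14 | day 43-44 | 13-14 days |
| Seropositive, 10-day window | day 16-17 | day 46-47 | 16-17 days |
| Untreated | none | day 30 (assumed) | 0 |

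The gap is 6-17 days. At most that is 17/30 = 57% of a visit interval, or 17/270 = 6.3% of follow-up.

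**Step 2: mean shift of the SSAT arm.** Share treated × offset:
- 14-day offset: 0.30 × 14 = 4.2 to 0.70 × 14 = 9.8 days.
- 17-day offset: 0.30 × 17 = 5.1 to 0.70 × 17 = 11.9 days.

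In the control arm the shift is near zero.

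**Step 3: bound on the rate ratio with no drug effect.** Suppose the hazard is constant and events and person-time are counted over windows that differ by the mean shift. The rate ratio is then off by (270 + shift)/270 or its inverse:
- 4.2 days: 274.2/270 = 1.016, or 0.985.
- 11.9 days: 281.9/270 = 1.044, or 0.958.

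If instead each child is observed for nine months from his or her own anchor, window lengths are equal and only the calendar dates move.

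**Step 4: null simulation.** 60,000 children per arm, infection rate 1 per year, nine visits 30 days apart, a 14-day shift in half or all of the SSAT arm. Rate ratios (SSAT/control) by mean infection duration:

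| Origin, share shifted | 15 d | 30 d | 60 d | 120 d |
|---|---|---|---|---|
| Enrolment, half | 0.982 | 0.986 | 0.982 | 0.999 |
| Enrolment, all | 0.958 | 0.973 | 0.979 | 1.017 |
| Last dose, half | 1.013 | 1.014 | 1.026 | 1.012 |
| Last dose, all | 1.010 | 1.029 | 1.034 | 1.046 |

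A separate run with half the arm shifted gave rate ratios of about 0.99-1.03, and hazard ratios for first recurrence of about 0.95-0.99 with enrolment as origin. The infection rate and durations are assumptions, not protocol figures.

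**Step 5: the other reading.** If the sentence means one month after the treatment round ends, every child in a school is visited on the same date and the shift is 0 days. A round ending about day 14 puts the first visit at about day 44, which fits Month 2 in Appendix H.

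**The case against.** The strongest reply is that the protocol describes one calendar. Appendix H has a single schedule in which only the drug and safety rows depend on treatment. Appendix C shows one block of nine monthly samplings after enrolment. The synopsis and 6.3 follow all children in both arms for nine months, and the study ends in a mass survey of everyone. Read alongside these, 6.7 may simply mean that sampling starts a month after the treatment round. The day-30 date for untreated children appears nowhere in the protocol.

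Most of this stands. A reader might infer that visit dates and observation windows do differ systematically between the arms. The documents do not support that: it needs both a child-by-child reading and a separate anchor for the untreated, and neither is stated. A reader might also infer that treated children's nine samples cover a longer span. They do not: with equally spaced visits, first to ninth sample is eight intervals for everyone, and only the start moves. Nor does the split follow the arms cleanly, since with 30-70% seroprevalence a large part of the SSAT arm may have no last dose either.

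The lack of a stated time zero in 8.3 is not a fault in itself, because an analysis plan may set it. What remains is that the only written dating rule is conditional on treatment, 6.7 does not say it refers to the round, and its visit numbering differs from Appendix H.

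**Conclusion.** The point holds as an inconsistency that should be corrected, not as a demonstrated bias. The follow-up start in 6.7 is undefined for most children, tied to the intervention, and not reconciled with Appendix H.

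The consequence depends on the reading. Under a common calendar it is nil. Under the child-level reading, with untreated children timed from enrolment, first samples differ by about 6-17 days. With half the SSAT arm shifted by 14 days, the null rate ratio is about 0.98-1.03 and the null hazard ratio about 0.95-0.99 (enrolment origin). The wider rate-ratio range of 0.96-1.05 needs the whole SSAT arm shifted, which fits poorly with the 30-70% seroprevalence criterion. The direction for the rate ratio depends mainly on the origin chosen; for the hazard ratio with enrolment origin it favours SSAT.

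These sizes rest on constant hazard, an assumed infection rate and durations, and the seroprevalence proxy. A few percent would not by itself produce a positive trial, but it is avoidable and must be settled before sampling starts.

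**What to change.** Replace the sentence in 6.7 with one visit calendar for all randomised children in both arms, for example by school. Count visits from enrolment or randomisation, whatever treatment was received, and place the first visit after the serology-triggered courses have ended. About day 45 is one example consistent with Appendix H.

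Use the same visit labels in 6.7, 7.1.1 and Appendix H (months 1-9 or 2-10), and state whether the interval is a month or four weeks. State enrolment or randomisation as time zero for person-time and time-to-event in both arms.

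The cost is one sentence and consistent labels. No visit is added and no treatment changes, and visiting a whole school on one date should be easier in the field. The downside is that some treated children will be sampled a few days before or after exactly one month from their last dose.

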	
PCR.
 
(VII) To analyse hemoglobinopathies in schoolchildren using HemeChip by Gazelle (Hemex Health, USA)
 
Primary study endpoint: the proportional reduction of P. vivax incidence by PCR in children serologically screened relative to those receiving routine care during 9 months of active follow-up.
 
Secondary endpoints:
 
(I) Difference in the time-to recur of P. vivax by PCR in SSAT and control arms.
 
(II) Difference in the number of recurrent P. vivax by PCR in SSAT vs. control arms.
 
(III) Difference in the incidence of recurrent symptomatic P. vivax by LMF in SSAT vs control arms.
 
(IV) Seroconversion rate before and after intervention in SSAT and control arms.
 
(V) Sensitivity and specificity of POC antibody detection test vs. gold standard Luminex assay.
 
(VI) Adverse event (AE) and Severe Adverse Event (SAE) of high dose PQ in schoolchildren.
 
(VII) Hb level in Sahli's method, Standard G6PD (SD Biosensor Inc., ROK), and Gazelle® (Hemex Health, USA), in comparison with HemoCue (HemoCue AB, Angelholm, Sweden).
 
(VIII) Sensitivity and specificity of microscopic examination to detect parasitemia from the shallow skin vasculature of the ankle (light microscopy-skin/LMS) compared to standard microscopic (light microscopy-finger/LMF) and PCR.
 
(IX) Mean duration time of gametocyte in LMS and LMF
 
(X) Sensitivity and specificity of magneto-optical hemozoin detection (MOD) compared to standard malaria detection and PCR.
 
(XI) Hemoglobinopathy rate in schoolchildren

Study Site	Malaka regency, East Nusatenggara province, Indonesia.
Study Duration	January 2020 to January 2021
Number of Participants, Randomisation, and Treatment	
A total of 800 elementary schoolchildren and their households living at Malaka, West Timor.
 
Randomization and Treatment:
 
 
Participants will be randomized into two groups: (1) intervention group (SSAT; n=400) and (2) routine care group (n=400). All participants will be tested for presence of antibodies to a validated panel of P. vivax antigens and
 

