## 6.6. Enrolment

During enrolment, finger pricked blood samples will be collected from all participants. At this activity, body temperature will be recorded using infrared thermometers, body weight will be scaled, history of fever within 3 days and taking antimalarial drugs within last 2 weeks will be recorded. Finger pricked blood samples will be made into malaria blood smear and tested by POC Pv antibody rapid detection. A total of 400  $\mu$ L will be collected into microtainer tube containing EDTA to be sent to field laboratory, and separated for various tests, e.g. serology (Luminex), PCR, Hb, G6PD, and Hemex.

All participants' blood samples will be tested for the presence of antibodies to a validated panel of *P. vivax* antigens (using a gold-standard laboratory test) at the Eijkman Institute for Molecular Biology, Jakarta. Blood samples will be shipped every 2 days, and the result will be reported to the field team within no more than 1 week.

On site, blood slides will be Giemsa stained (see 7.3) and assessed by microscopy with 1000x magnification. Screening for G6PD deficiency will be performed quantitatively by Standard G6PD (SD Biosensor, ROK) with the cut off of 4 U/g Hb (male) or 6 U/g Hb (female) on the same day of blood collection. Hb level will be measured using HemoCue and Hb Sahli. Other substudies (LMS, hemozoin detection, hemoglobinopathy) will also be conducted (see 6.10)

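### Before the final visit, the symptomatic P. vivax endpoint depends on fever reports from people who can see which children were treated

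*Protocol*

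**What the plan says.** **Treatment at enrolment.** Under Section 6.3, SSAT children positive by Luminex or smear "will receive supervised treatment (direct observation) with high dose PQ (daily 1 mg/kg BW) for 7 days". In the control arm, "only symptomatic individuals found *P. vivax* positive by Giemsa stained microscopic examination will receive the same regimen". Section 6.8 adds daily haemoglobin and urine checks for treated children. The text describes no placebo, sham course or masked assessor, and never states masking status.

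**Who knows.** Section 6.6 says of the Luminex assay that "the result will be reported to the field team within no more than 1 week". The screening form in Appendix J puts the child's name, serology and microscopy on one row. The text under Figure 1 asks health-centre staff to help in the field, and Section 6.7 has them give all follow-up treatment.

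**What triggers a smear.** Section 6.7: "malaria blood smear will be made only from participants with clinical symptoms suggestive for malaria". Section 6.3 defines the symptoms as a temperature of at least 37.5 °C and/or a fever history within 3 days. Such children "will be examined by Giemsa stained microscopy on site, and treated if positive (any species) according to national guideline (unsupervised".

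**What counts as an event.** In Section 8.3, symptomatic recurrence "is defined as LMF positive with fever" of at least 37.5 °C, or with a 3-day fever history.

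**What does not depend on symptoms.** Section 6.3 takes blood for PCR from every child each month, and smears every child at the last visit.

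**The concern.** Endpoint III is the only efficacy endpoint that measures clinical disease. Before the last visit, an event needs measured or reported fever, then a smear, then a positive slide. Fever history comes from the child or family and is recorded by staff. Either may know that a child took a week of observed drug with daily checks. Serology-triggered courses occur only in the SSAT arm, so visible treatment is associated with arm.

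If a fever in a child thought to be cleared is mentioned or pursued less often, no smear exists and no later analysis can recover the event. Endpoint III could then show a reduction that comes partly from reporting.

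The same smear decides who receives follow-up antimalarials, which for P. vivax include primaquine (Appendix B, Table 3). Unequal smearing could therefore also mean unequal treatment during follow-up.

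**Working it through.** **1. The plan's own figure.** There is none for endpoint III. The power of more than 90% with 350 children per arm (Section 8.2) concerns infection by PCR. It comes from a simulation whose effect size is not in the text, and it does not bear on this point.

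**2. Which events can be lost.** A measured temperature of at least 37.5 °C triggers a smear by itself. Only episodes identified by history alone, and any decision not to pursue symptoms, are sensitive to who knows what.

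**3. Size with no true effect.** All three inputs are assumptions; the documents give none of them.

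- s = share of SSAT symptomatic events that arise in treated children, 0.5 to 0.8
- h = share of those events identified by history alone, 0.5 to 0.8
- r = reporting in treated relative to untreated children, 0.7 to 0.9

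The share of SSAT events lost is s × h × (1 − r). If control reporting is unchanged, the observed rate ratio is 1 − s × h × (1 − r).

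| Case | s | h | r | Rate ratio |
|---|---|---|---|---|
| Mildest | 0.5 | 0.5 | 0.9 | 1 − 0.025 = 0.975 |
| Middle | 0.5 | 0.6 | 0.8 | 1 − 0.06 = 0.94 |
| All inputs at their worst | 0.8 | 0.8 | 0.7 | 1 − 0.192 = 0.808 |

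If treated families reported more fever instead, the sign would reverse. The mirror image of the middle case is 1 + 0.5 × 0.6 × 0.2 = 1.06.

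**4. Cross-check with a figure from the protocol.** Section 6.2 admits schools with seroprevalence of 30–70%, a rough guide to the share of SSAT children treated. With an assumed overall reporting shortfall d of 10–30% in treated children, the rate ratio is 1 − s × d:

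- s = 0.3: 0.97 to 0.91
- s = 0.5: 0.95 to 0.85
- s = 0.7: 0.93 to 0.79

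A true rate ratio of 0.70 would appear as 0.70 × 0.97 = 0.68 down to 0.70 × 0.79 = 0.55. With no difference in reporting (d = 0), the observed ratio equals the true one.

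**5. PCR endpoints.** Sampling is monthly in all children (Sections 6.3 and 7.1.1, Appendix H), so detection cannot differ by arm through this route. What remains is a change in later infections through unequal smear-triggered treatment. If controls had more smears and more treatment, the PCR comparison would move toward no difference. The documents give no basis for a figure.

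**6. The trigger is stated inconsistently.**

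| Item | One place | Another place |
|---|---|---|
| Fever-history window | Sections 6.3 and 8.3: 3 days | Appendix J follow-up form: last week |
| Smears before the last visit | Section 6.7: symptomatic children only; Section 7.1.1: only the 400 µL sample in months 1–8 | Appendix H: LMF marked at every monthly visit |

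The second conflict bears directly on the concern. If every child were smeared monthly, no event would be lost for want of a slide, although fever history would still decide whether a positive slide counts as symptomatic.

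**The case against.** The protocol already limits the problem in several ways. Appendix H schedules temperature and fever history for every child at each monthly visit, so fever is not left to volunteered reports; the freer route is the unscheduled rows on the follow-up form. That form has no arm, serology or treatment column. Specimen labels carry only school, subject and visit codes (Section 8.1). An event needs a positive slide read by a certified microscopist and cross-checked in Jakarta (Section 7.3). Visible treatment is an imperfect marker of arm: untreated seronegative SSAT children look like controls, and some controls take the same course. All of this stands. It makes the bias smaller but does not remove it. A form without an arm column does not mask a person who supervised the course, and nothing says slide readers lack treatment information.

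It can also be said that symptom-triggered microscopy is what routine care consists of, and that sensitivity analyses belong in an SAP. The first is true, and the proposal leaves the trigger alone. The second is fair for the analysis, but who records fever and what readers know are conduct rules, and no SAP can recover smears that were never made.

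Four stronger readings are tempting, and the documents do not support them:

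- That detection of later infections, and so the primary endpoint, differs by arm. Monthly PCR in all children rules this out.
- That endpoint III rests only on symptom-triggered smears. At the last visit every child is smeared.
- That a spurious reduction of about 19% should be expected. That figure sets all three assumed inputs to their worst values.
- That the bias must favour SSAT. Families of treated children might instead be more watchful.

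**Conclusion.** The concern holds for endpoint III before the final visit. Treatment is visible, no masking is described, serology reaches the field team, and a reported fever history alone can open or close the way to an event. The absence of masking is inferred from an observed course without placebo; the protocol does not state it, and Figure 1 is not shown.

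The size is unknown. With no true effect and the assumptions above, the rate ratio would be about 0.98 to 0.81, with 0.94 at middle values; the cross-check gives a similar 0.97 to 0.79. Under-reporting in treated children would favour SSAT, but that direction is plausible rather than established. The PCR endpoints are open only to the indirect, unquantified effect of unequal follow-up treatment. The point merits a change because the remedy is cheap and endpoint III carries the clinical claim.

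**What to change.** - **Section 7.3:** state that slides are read, in the field and at the Jakarta cross-check, from ID-only labels without arm, serology or treatment record.
- **Section 6.7:** state that, where existing staffing allows, temperature and fever history are recorded with one standard question by staff who work by ID from the follow-up form and have no arm, serology or treatment information.
- **Section 8.3:** add a sensitivity analysis of endpoint III that counts qPCR-positive P. vivax with a measured temperature of at least 37.5 °C at a scheduled visit.
- **Sections 6.3, 6.7, 7.1.1 and 8.3, Appendices H and J:** reconcile the fever-history window and the smear schedule. Both also govern follow-up treatment, so which version applies is for the investigators to settle.

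The cost is protocol wording and some organisation of staff; no new samples are needed. The sensitivity analysis will have fewer events, will miss episodes between visits, and will count some unrelated fevers in PCR-positive carriers (Section 8.2 cites a PCR prevalence of about 20%). It also remains exposed to any unequal follow-up treatment. It should therefore stand beside endpoint III and not replace it.
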